	
epilepsy.
 
• Subjects with any bladder abnormality that would affect the urinary flow through the lower urinary tract including symptoms of a urinary tract infection, abnormal bladder capacity (e.g., >300 cc), post void residual volume >200 cc, spastic bladder, vesico-ureteral reflux or bladder stones.• Subjects with a blood clotting disorder or who are taking anti-coagulant medications.• Subjects who have previously had any urogynaecological related surgery that would affect the pelvic floor muscles or urinary flow through the urethra (excluding hysterectomy).• Subjects who have previously had pelvic floor radiation.• Subjects who have previously been treated for stress incontinence with injectable bulking agents and/or vaginal probes within the past 6 months.• Subjects with a clinical diagnosis of prolapse greater than Stage 2.• Subjects who are pregnant or could be pregnant.• Subjects who are less than 6 months post-partum or who are lactating.• Subjects who have any conductive intra-uterine devices or metal implants in the pelvic area, including hip and lumbar spine.• Subjects with pelvic pain or fibromyalgia or paravaginal defect.• Subjects with an active implanted medical device (e.g. pacemaker, insulin pump) or conditions that may be adversely affected by electrical stimulation (e.g. cardiac arrhythmias).• Subjects with a current or active history of pelvic cancer and/or subjects with a life expectancy of less than 12 months.• Subjects who are currently involved in any injury litigation claims.• Subjects who have participated in a clinical study in the last 3 months or any previous clinical study with Bio-Medical Research Ltd.• Subjects who have been committed to an institution by virtue of an order issued either by the courts or by an authority.
Study Sites:	Approximately 12 USA sites
Number of subjects planned:	Approximately 180 subjects (90 subjects per group).
Target population:	The patient population will be females with stress incontinence.

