6.3 Exclusion Criteria

1. Subjects who have an existing medical condition that would compromise their participation in the study, e.g. reduced sensory perception in the contact area of the stimulation electrodes; scars or vaginal tissue wounds, lesions or inflamed/infected areas in the contact area of the stimulation electrodes; vaginal bleeding between menstrual periods; uncontrolled diabetes.
2. Subjects who have a physical condition that would make them unable to perform the study procedures, e.g. pelvic or hip surgery within the past 6 weeks.
3. Subjects who have been diagnosed with Chronic Obstructive Pulmonary Disease (COPD).
4. Subjects with a history of an underlying neurological condition, e.g. Multiple Sclerosis, Parkinson's disease, epilepsy.
5. Subjects with any bladder abnormality that would affect the urinary flow through the lower urinary tract including signs or symptoms of an active urinary tract infection, abnormal bladder capacity (e.g., $>300 \text{ cc}$), post void residual volume $>200 \text{ cc}$, spastic bladder, vesico-ureteral reflux or bladder stones.
6. Subjects with a blood clotting disorder or who are taking anti-coagulant medications.

7. Subjects who have previously had any uro-gynaecological related surgery that would affect the pelvic floor muscles or urinary flow through the urethra (excluding hysterectomy).
8. Subjects who have previously had pelvic floor radiation.
9. Subjects who have previously been treated for stress incontinence with injectable bulking agents and/or vaginal probes within the past 6 months.
10. Subjects with a clinical diagnosis of prolapse greater than Stage 2.
11. Subjects who are pregnant or could be pregnant.
12. Subjects who are less than 6 months post-partum or who are lactating.
13. Subjects who have any conductive intra-uterine devices or metal implants in the pelvic area, including hip and lumbar spine.
14. Subjects with pelvic pain or fibromyalgia or paravaginal defect.
15. Subjects with an active implanted medical device (i.e. pacemaker, insulin pump etc.) or conditions that may be adversely affected by electrical stimulation (e.g. cardiac arrhythmias).
16. Subjects with a current or active history of pelvic cancer and/or subjects with a life expectancy of less than 12 months.
17. Subjects who are currently involved in any injury litigation claims.
18. Subjects who have participated in a clinical study in the last 3 months or any previous clinical study with Bio-Medical Research Ltd.

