test). The data from this test will not be used for analysis purposes, it is only to allow patients to practice the stress test. Further details of the stress test protocol and instructions for the Investigator and subject are provided in Appendix III.

- Record any cough or cold symptoms.
- Record any adverse events.

Prior to leaving the clinic, subjects will also be provided with the following:

- A 7-day voiding diary to complete seven days prior to the Visit 2 (baseline) appointment.
- Pre-weighed incontinence pads in a sealed bag to complete the 24-hour pad collection for three days prior to the Visit 2 (baseline) appointment.

The subject will then be asked to return the 7-day voiding diary and incontinence pads in the same sealed bag to the clinic at Visit 2. Any subjects menstruating during the three days prior to Visit 2 will also be asked to record this on the voiding diary. Any subjects who have sexual intercourse during this three day period will be asked to expel any fluid post-intercourse and also record this on the voiding diary.

8.10 Baseline Assessments – Visit 2

On the subject's return to the clinic to return the 7-day voiding diary and incontinence pads, the following information/procedures will be recorded:

- Complete the Incontinence Quality of Life Questionnaire (I-QOL) (patient quality of life questionnaire).
- Complete the Pelvic Organ Prolapse/Urinary Incontinence Sexual Questionnaire (PISQ-IR).
- Complete a standardized stress test to evaluate amount of urine lost following a standardized bladder-filling protocol verified by ultrasound bladder scanning (provocative pad weight test). This assessment will be used to determine the subject's eligibility to participate. Further details of the stress test protocol and instructions for the Investigator and subject are provided in Appendix III.
- Number of incontinence episodes/day from 7-day voiding diary.
- Number of pads used/day from 7-day voiding diary.
- Mean weight of urine leaked during three consecutive 24-hour periods at home (difference in post- and pre-weight incontinence pads) (24-hour pad weight test). Severity score will be assessed as dry (less than 2g), mild (greater or equal to 2g and less than 10g), moderate (greater or equal to 10g and less than 50g) and severe (greater than 50g) (O'Sullivan, 2004).
- Record any medication use or changes in medication since the last visit.
- Record any cough or cold symptoms since the last visit.

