14.3 Appendix III. Stress Test Protocol

Where possible the assessment will be performed by the same examiner each time for the duration of the study, for a given subject, as follows:

Balance Calibration

- All pad weights will be weighed using a balance supplied by the Sponsor.
- On each day of the assessments and prior to the weighing of the pads, the balance will be calibrated using calibration weight supplied by the Sponsor and the details recorded to verify the balance is operational.
- All zip-lock freezer bags will be weighed in a container to minimise any weight fluctuations.

Bladder Filling Protocol

- Prior to the stress 1h pad test, a pad (moderate POISE) is placed in a zip-lock bag (Weight A).
- Subjects are advised to attend the clinic with a comfortably full bladder.
- Following the pregnancy test, the subject voids the bladder and then drinks 500 mL of water.
- The subject is instructed not to go to the toilet and waits for 1 hour.
- After approximately 1 hour, the Investigator will check that natural diuresis has resulted in a bladder volume of more than 250mL as confirmed by ultrasound or other appropriate method.
- If the bladder volume is not 250mL or more, the subject will be instructed to wait for approximately 30 minutes when it will be re-checked. The exact bladder volume will be recorded.
- On confirmation the bladder volume is 250mL or more, the pad is handed to the subject in the bag and the subject is instructed to attach the pad in their underwear and put the packaging and pad liner back in the zip-lock freezer bag.

Stress Test Protocol is a modified version of the provocative test determined by Bo, 1999.

- The metronome is set to 132bpm.
- The subject is instructed not to contract their pelvic floor muscles but to ‘leak’ as usual.
- The subject is then instructed to run on the spot (with their knees bent) for 30 seconds followed immediately by 30 seconds of jumping jacks (with their arms straight and legs as wide as they can).
- The subject will be encouraged to keep pace with the metronome during the test. If the subject cannot, it will be documented how much of the protocol was completed to establish their baseline. This exact test must then be used in subsequent follow up visits.
- The subject will be asked to sit and stand 10 times from a chair, (the same chair to be used in repeated tests)
- The subject will cough forcefully 10 times
- The subject will pick an object, e.g a pencil, off the floor 5 times.

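### Exclusion criterion 5 gives bladder capacity above 300 cc as its example of an abnormality, yet the stress test behind eligibility and the primary endpoint accepts any volume from 250 mL upward

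*Protocol*

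**What the plan says.** **The exclusion.** Criterion 5 in Protocol Section 6.3, repeated in the synopsis, covers "Subjects with any bladder abnormality that would affect the urinary flow through the lower urinary tract". Several conditions are listed as included. One is "abnormal bladder capacity (e.g., >300 cc"; others are a post-void residual above 200 cc and "spastic bladder, vesico-ureteral reflux or bladder stones".

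**The filling rule.** In Protocol Appendix III, "the subject voids the bladder and then drinks 500 mL of water" and does not use the toilet for an hour. The examiner then checks that "natural diuresis has resulted in a bladder volume of more than 250mL as confirmed by ultrasound" or another suitable method. "If the bladder volume is not 250mL or more, the subject will be instructed to wait for approximately 30 minutes", after which the volume is checked again. The exact volume is to be recorded. The test then begins: "On confirmation the bladder volume is 250mL or more, the pad is handed to the subject". No maximum volume is stated.

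**Where the test is used.** It is practised at screening (Section 8.9) and repeated at Weeks 4, 12 and 26. Of the baseline test, Section 8.10 says: "This assessment will be used to determine the subject's eligibility to participate". Section 5.1 takes the primary endpoint from the Week 12 test.

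**What follows from failing a criterion.** Section 8.7 stops any subject who fails any element of the criteria from going further. Protocol Section 10.1 and SAP Section 2.1 make meeting the entry criteria a condition of the per-protocol population. The SAP also requires that there be no significant protocol deviations.

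**The concern.** The 300 cc example is the only figure that tells a site what capacity counts as abnormal, and its stated direction is upward. The filling procedure, required before every stress test, accepts and documents volumes in that same upward range. The protocol can therefore produce a record that qualifies a woman under Appendix III and at the same time matches the example in criterion 5.

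Two things are at stake. The first is consistent eligibility across approximately 12 sites: one may screen out a woman who scans above 300 mL and another may enrol her, each with support in the text. The second is the per-protocol population, which supports the non-inferiority claim. Because volumes are recorded, anyone checking entry criteria afterwards could ask whether an enrolled woman with a volume above 300 mL met criterion 5.

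**Working it through.** The plan states no figure to reproduce here. The check compares two limits.

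**Inputs**
- Capacity example: above 300 cc, which is 300 mL (synopsis; Section 6.3, criterion 5).
- Filling rule: at least 250 mL, no maximum (Appendix III). The appendix has both more than 250 mL and 250 mL or more; the difference does not matter here.
- Post-void residual: excluded only above 200 cc (same criterion).

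**Step 1. Link volume to capacity.** Let V be the scanned volume and C the capacity. A bladder seen to hold V has C ≥ V. The scan is a lower bound on capacity, not a measurement of it.

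**Step 2. Compare by range of V.**

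| Scanned volume | Appendix III | Criterion 5 example | Conflict? |
|---|---|---|---|
| V < 250 mL | Wait and re-check | Scan does not show C > 300 | No; this is an ordinary test minimum |
| 250 ≤ V ≤ 300 mL | Test proceeds | Scan does not show C > 300 | No |
| V > 300 mL | Test proceeds | C ≥ V > 300, the range named as abnormal | Yes |

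The conflict is confined to the last row, and that row has no upper end.

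**Step 3. Can the last row occur?** Nothing in Appendix III prevents it. The wait is about an hour, with a re-check about 30 minutes later if needed, and no volume is declared too high. As a boundary case, a woman at the permitted residual of 200 mL reaches the figure after 300 − 200 = 100 mL of new urine. This shows only that such volumes are possible; it says nothing about how often they arise.

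**Step 4. Is there another source for capacity?** Sections 8.9 and 8.10 and the Appendix I schedule list no capacity measurement. History and examination are available at screening. The pre-test scan is the one scheduled objective reading that bears on capacity.

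**Step 5. Trace the effect on each population.**
- *Enrolment.* The screening and baseline scans both precede randomisation (Section 8.8 requires all baseline assessments first). A site applying the example strictly would stop the subject under Section 8.7.
- *Intention to treat.* This is all randomised subjects, so an enrolled woman stays in whatever her volume. The SAP's modified version removes only those who never used the device.
- *Per protocol.* Meeting the entry criteria is required, so a recorded volume above 300 mL gives grounds for a query. Removal is not automatic: under SAP Section 2.1 the Sponsor/CRO reviews a listing and documents exclusions before unblinding.

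**The case against.** The best reply is that criterion 5 has no 300 cc cut-off. The condition is an abnormality that would affect urinary flow, and the capacity figure is offered as an example, whereas the neighbouring post-void residual figure is a direct limit. With no capacity measurement scheduled, the natural course is to judge the criterion from history and examination. The stated purpose of the scan is to confirm filling, and no section tells sites to use it as a capacity check. A volume above 300 mL does not in itself show disturbed flow. Further, the criterion and the filling rule are the same in both arms, intention to treat is primary, and per-protocol exclusions are settled before unblinding.

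Most of this stands, and it limits the point. It rules out three stronger readings that a reader might infer:

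- *Only women with a capacity of 250 to 300 mL, a 50 mL window, can qualify.* The subtraction is right, but it joins a test-day minimum to an illustrative value. Neither section states an admissible range, and a minimum filling volume does not conflict with the exclusion.
- *The 500 mL drink already exceeds the limit.* Water drunk is not bladder volume. Appendix III itself provides for women still below 250 mL after about an hour.
- *Sites must either ignore the exclusion or drop these women.* A site can apply the criterion as worded by judging whether there is an abnormality affecting flow.

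What the reply does not remove is the inconsistency. Judgement explains how sites may cope, but the one figure given to guide that judgement labels as abnormal a range that the protocol's own test accepts.

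**Conclusion.** The point holds as an inconsistency between criterion 5 and Appendix III, limited to scanned volumes above 300 mL. It bears on how uniformly eligibility is judged and on possible queries about the supportive per-protocol population. It does not directly affect the primary intention-to-treat comparison, and nothing in the documents indicates a bias between arms.

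Its size cannot be given: the documents contain no distribution of bladder volumes under this filling procedure, so the share of women above 300 mL is unknown. The conclusion rests on two premises: that a volume held is a lower bound on capacity, and that the example is printed with its intended direction. If the direction is a slip, the conflict above 300 mL disappears once it is corrected, but the text still has to be corrected. The change is worth making because it is cheap and eligibility depends on it; it does not call the design into question.

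**What to change.** Reconcile exclusion criterion 5 with Appendix III, in both the synopsis and Section 6.3. Check the intended direction and value of the capacity example, then restate it so that a volume acceptable for the stress test is not by itself an exclusion. Which threshold is right, and whether one is needed, is for the sponsor's clinicians.

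If women have already been enrolled with recorded volumes above 300 mL, the review of per-protocol criteria that SAP Section 2.1 already plans before unblinding should state how they are treated.

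The cost is one line of amended text in two places. No change to the sample size, the endpoint or the analysis model follows from it.

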2.1 Background

The International Continence Society (ICS) defines urinary incontinence as the involuntary loss of urine that is a social or hygienic problem and one that is objectively demonstrable. Stress urinary incontinence (SUI) is urinary incontinence during physical activities that increase intra-abdominal pressure such as coughing, sneezing or lifting. Stress urinary incontinence often leads to patients limiting their participation in social activities, which in turn has a subsequent impact on a person's quality of life. While some seek surgical intervention, physical therapy is seen as the first treatment option in this often under-reported condition. There are a number of treatments available to the therapist. Most women treated for stress urinary incontinence will have been introduced to pelvic floor muscle training exercises however adjunctive approaches such as biofeedback, vaginal weights and electrical stimulation are also treatment options.

Bo (2004) described the goal of physical therapy in the treatment of stress urinary incontinence as an attempt to improve pelvic floor muscle function by increasing strength, coordination, speed and endurance. The effect of these training adaptations is the maintenance of an elevated position of the bladder neck during raised intra-abdominal pressures and a subsequent adequate urethral closing force as described by Ashton-Miller et al. (2001).

Castro (2008) reported a significant decrease in urine lost during pad tests and in the number of stress urinary episodes, as well as a significant improvement in the quality of life, in subjects who underwent a programme of pelvic floor exercises, electrical stimulation or use of vaginal weights compared to a control group. In this study there was no observed difference between treatment groups suggesting each intervention to be equally effective. While it is reported that these interventions can be effective in the treatment of stress urinary incontinence the issues of technique, comfort of treatment and compliance with treatment are often limiting factors that impact patient outcomes. This has motivated the search to identify an electrical stimulation treatment modality that ensures satisfactory recruitment of the pelvic floor muscles and that is easy to administer and more comfortable for the patient. This resulted in the development of a novel electrical stimulation (ES) device that includes a wired garment which locates a set of skin contact electrodes around the pelvic area.

A pilot study (n=9) with this novel ES system (first generation device called UCD RS device) conducted at University College Dublin has shown improved outcomes (Maher and Crowe, 2008) following an 8 week treatment programme. In particular, subjects using the ES system achieved a significant decrease in symptoms when compared to the control group. At Week 1 all subjects could perform appropriate volitional contractions of their pelvic floor muscle in standing but more importantly there was a reported 87.43% decrease in leakage. At Week 8, subjects reported a 97.71% decrease in leakage ($P<0.01$) and the IIQ-7 and Modified Oxford scores also changed significantly ($P<0.01$).

A pilot study (n=19) has recently been completed in Germany at St. Hedwig Krankenhaus (Soeder and Tunn, 2013) which looked at a 12 week treatment programme with the second generation device (called Inko RS device). Sixteen subjects completed baseline measurements while 14 and 13 subjects completed the 12-week and 26-week assessments, respectively. Mean (SD) urine leakage on the 1-hour and 24-hour pad weight tests improved ($p<0.05$) from 41.6g (43.92) to 5.8g (13.19) and 21.8g (19.41) to 5.6g (5.16) respectively after completion of the 12 week programme. These improvements were substantially retained at the 26 week point. In

addition, 57% of subjects were classified as dry at the 12 week point, based on a 1-hr stress test result of less than 2g. This coincided with enhanced quality of life scores during and following the intervention period. Secondary measures also identified a reduction ($p<0.05$) in the number of leakages experienced per day, from 2.5 (2.81) at baseline to 1.2 (2.28) at 26 weeks with an improvement in the modified Oxford scale. One patient suffered an allergic skin reaction to the hydrogel electrodes.

A randomised study (n=51) is currently ongoing in Germany at three sites with the third generation device (Neurotech Vital device). The purpose of this study is to test whether a 12-week programme with the Neurotech Vital device significantly improves the symptoms of stress incontinence in female subjects compared to a modified Neurotech Vital device (sham device). In addition, the long term effects of a 12-week treatment with the Neurotech Vital device will be evaluated.

The purpose of this proposed study is to conduct a pivotal study comparing the Neurotech Vital Compact device (fourth generation device) to an FDA 510(k) approved predicate device (itouch Sure Pelvic Floor Exerciser) to generate clinical data to submit to the FDA to obtain regulatory clearance.

2.2 Rationale of Study Population

The clinical study is designed to be prospective to ensure that the population is representative of the type of population for which the Neurotech Vital Compact device is intended to treat. Subjects will be drawn from clinics focusing on this type of treatment. These clinics may advertise using an approved advertisement to recruit additional subjects.

The patient population will be female patients identified by the clinic as seeking treatment for urinary stress incontinence. These patients will have previously tried volitional pelvic floor muscle exercises and have been unsuccessful in their attempts to alleviate their symptoms.

2.3 Rationale of Neurotech Vital Compact Device

The research evidence supporting the use of electrical stimulation (ES) in pelvic floor neuromuscular rehabilitation for stress urinary incontinence (SUI) is somewhat equivocal. While some studies (Castro, 2008; Sand, 1995) have shown a beneficial effect of ES that is comparable to other conservative interventions, there are other studies which have failed to show a clear benefit (Bo, 1999). There has been a lack of homogeneity in the study designs and most especially in the equipment used. Most studies have used one or other of the commercially available trans-vaginal ES systems and little information has been provided as to the effectiveness of the particular system used in activating the target muscle group. A further difficulty with transvaginal ES is that some patients object to using the intra-vaginal probe electrodes. A novel form of ES for pelvic floor stimulation has been developed which utilises an array of external electrodes and this is believed, based on observation using pelvic floor (PF) ultrasonography, to deliver much greater levels of PF muscle activation than the transvaginal approach.

Thus in this study we will be using the Neurotech Vital Compact device to deliver neuromuscular electrical stimulation (NMES) to the pelvic floor muscles via an arrangement of external electrodes optimally positioned to successfully stimulate these muscles and held in place by a garment to facilitate good skin contact and repeatability of positioning. The

Neurotech Vital Compact device is the fourth generation of the device which has been developed using the same technology as the UCD RS device (first generation device) and Inko RS device (second generation device).

Previous experience indicates that NMES muscle training effects are cumulative over a period of time and early indication using the device for five days with two rest days in a 7 day period for a stipulated period of weeks provides an optimum effect. A treatment regimen has therefore been selected where patients self-administer 30 minutes of treatment for 5 days each week for a 12 week period. It is anticipated that most patients would respond in a quicker time with short term beneficial results within 8 weeks, however, a 12-week treatment period is more likely to result in cumulative muscle training effects. Patients will control the intensity of stimulation within predefined levels from the control unit which will also maintain an electronic record of usage times and intensity to check for compliance.

